11.2.2. Severity / Intensity

For both AEs and SAEs, the Investigator must assess the severity / intensity of the event.

The severity / intensity of AEs will be graded based upon the subject's symptoms according to the current active minor version of the Common Terminology Criteria for Adverse Events (CTCAE, Version 4.03);

http://ctep.cancer.gov/protocolDevelopment/electronic_applications/ctc.htm#ctc_40

AEs that are not defined in the CTCAE should be evaluated for severity / intensity according to the following scale:

Grade 1 = Mild – transient or mild discomfort; no limitation in activity; no medical intervention/therapy required

Grade 2 = Moderate – mild to moderate limitation in activity, some assistance may be needed; no or minimal medical intervention/therapy required

Grade 3 = Severe – marked limitation in activity, some assistance usually required; medical intervention/therapy required, hospitalization is possible

Grade 4 = Life threatening – extreme limitation in activity, significant assistance required; significant medical intervention/therapy required, hospitalization or hospice care probable

Grade 5 = Death - the event results in death

The term "severe" is often used to describe the intensity of a specific event (as in mild, moderate or severe myocardial infarction); the event itself, however, may be of relatively minor medical significance (such as severe headache). This criterion is *not* the same as "serious" which is based on subject/event *outcome* or *action* criteria associated with events that pose a threat to a subject's life or functioning.

The term "severe" is often used to describe the intensity of a specific event (as in mild, moderate or severe myocardial infarction); the event itself, however, may be of relatively minor medical significance (such as severe headache). This criterion is *not* the same as "serious" which is based on subject/event *outcome* or *action* criteria associated with events that pose a threat to a subject's life or functioning.

Seriousness, not severity, serves as a guide for defining regulatory obligations.

11.2.3. Causality

The Investigator must determine the relationship between the administration of IP and the occurrence of an AE/SAE as Not Suspected or Suspected as defined below:

Not suspected:	Means a causal relationship of the adverse event to IP administration is unlikely or remote , or other medications, therapeutic interventions, or underlying conditions provide a sufficient explanation for the observed event.
Suspected:	Means there is a reasonable possibility that the administration of IP caused the adverse event. "Reasonable possibility" means there is evidence to suggest a causal relationship between the IP and the adverse event.

Causality should be assessed and provided for every AE/SAE based on currently available information. Causality is to be reassessed and provided as additional information becomes available.

If an event is assessed as suspected of being related to a comparator, ancillary or additional IP that has not been manufactured or provided by Celgene, please provide the name of the manufacturer when reporting the event.

11.2.4. Duration

For both AEs and SAEs, the Investigator will provide a record of the start and stop dates of the event.

11.2.5. Action Taken

The Investigator will report the action taken with IP as a result of an AE or SAE, as applicable (eg, discontinuation, interruption, or reduction of IP, as appropriate) and report if concomitant and/or additional treatments were given for the event.

11.2.6. Outcome

The investigator will report the outcome of the event of both AEs and SAEs. All SAEs that have not resolved upon discontinuation of the subject's participation in the study must be followed until recovered, recovered with sequelae, not recovered or death (due to the SAE).

11.3. Abnormal Laboratory Values

An abnormal laboratory value is considered to be an AE if the abnormality:

- results in discontinuation from the study;
- requires treatment, modification/ interruption of IP dose, or any other therapeutic intervention; or
- is judged to be of significant clinical importance, eg, one that indicates a new disease process and/or organ toxicity, or is an exacerbation or worsening of an existing condition.

Regardless of severity grade, only laboratory abnormalities that fulfill a seriousness criterion need to be documented as a serious adverse event.

If a laboratory abnormality is one component of a diagnosis or syndrome, then only the diagnosis or syndrome should be recorded on the AE page/screen of the eCRF. If the abnormality was not a part of a diagnosis or syndrome, then the laboratory abnormality should be recorded as the AE. If possible, the laboratory abnormality should be recorded as a medical term and not simply as an abnormal laboratory result (eg, record thrombocytopenia rather than decreased platelets).

11.4. Pregnancy

All pregnancies or suspected pregnancies occurring in either a female subject or partner of a male subject are immediately reportable events

11.4.1. Females of Childbearing Potential

Pregnancies and suspected pregnancies (including a positive pregnancy test regardless of age or disease state) of a female subject occurring while the subject is on IP, or during the course of the study, are considered immediately reportable events. IP is to be discontinued immediately. The pregnancy, suspected pregnancy, or positive pregnancy test must be reported to Celgene Drug Safety immediately by facsimile, or other appropriate method, using the Pregnancy Initial Report Form, or approved equivalent form.

The female subject should be referred to an obstetrician-gynecologist, preferably one experienced in reproductive toxicity for further evaluation and counseling.

The Investigator will follow the female subject until completion of the pregnancy, and must notify Celgene Drug Safety immediately about the outcome of the pregnancy (either normal or abnormal outcome) using the Pregnancy Follow-up Report Form, or approved equivalent form.

If the outcome of the pregnancy was abnormal (eg, spontaneous abortion), the Investigator should report the abnormal outcome as an AE. If the abnormal outcome meets any of the serious criteria, it must be reported as an SAE to Celgene Drug Safety by facsimile, or other appropriate method, within 24 hours of the Investigator's knowledge of the event using the SAE Report Form, or approved equivalent form.

All neonatal deaths that occur within 28 days of birth should be reported, without regard to causality, as SAEs. In addition, any infant death after 28 days that the Investigator suspects is related to the in utero exposure to the IP should also be reported to Celgene Drug Safety by facsimile, or other appropriate method, within 24 hours of the Investigator's knowledge of the event using the SAE Report Form, or approved equivalent form.

11.4.2. Male Subjects

If a female partner of a male subject taking investigational product becomes pregnant, the male subject taking IP should notify the Investigator, and the pregnant female partner should be advised to call their healthcare provider immediately.

11.5. Reporting of Serious Adverse Events

Any AE that meets any criterion for an SAE requires the completion of an SAE Report Form in addition to being recorded on the AE page/screen of the eCRF. All SAEs must be reported to Celgene Drug Safety within 24 hours of the Investigator's knowledge of the event by facsimile, or other appropriate method, using the SAE Report Form, or approved equivalent form. This instruction pertains to initial SAE reports as well as any follow-up reports.

The Investigator is required to ensure that the data on these forms is accurate and consistent. This requirement applies to all SAEs (regardless of relationship to IP) that occur during the study (from the time the subject signs informed consent until the last study visit) and any SAE made known to the Investigator at anytime thereafter that are suspected of being related to IP. SAEs occurring prior to treatment (after signing the ICF) will be captured.

The SAE report should provide a detailed description of the SAE and include a concise summary of hospital records and other relevant documents. If a subject died and an autopsy has been performed, copies of the autopsy report and death certificate are to be sent to Celgene Drug

Safety as soon as these become available. Any follow-up data should be detailed in a subsequent SAE Report Form, or approved equivalent form, and sent to Celgene Drug Safety.

Where required by local legislation, the Investigator is responsible for informing the IRB/Ethics Committee (EC) of the SAE and providing them with all relevant initial and follow-up information about the event. The Investigator must keep copies of all SAE information on file including correspondence with Celgene and the IRB/EC.

11.5.1. Safety Queries

Queries pertaining to SAEs will be communicated from Celgene Drug Safety to the site via facsimile or electronic mail. The response time is expected to be no more than five (5) business days. Urgent queries (eg, missing causality assessment) may be handled by phone.

11.6. Expedited Reporting of Adverse Events

For the purpose of regulatory reporting, Celgene Drug Safety will determine the expectedness of events suspected of being related to PDA-002 based on the Investigator Brochure.

In the United States, all suspected unexpected serious adverse reactions (SUSARs) will be reported in an expedited manner in accordance with 21 CFR 312.32.

Celgene or its authorized representative shall notify the Investigator of the following information.

- Any AE suspected of being related to the use of IP in this study or in other studies that is both serious and unexpected (ie, SUSAR);
- Any finding from tests in laboratory animals that suggests a significant risk for human subjects including reports of mutagenicity, teratogenicity, or carcinogenicity.

Where required by local legislation, the Investigator shall notify his/her IRB/EC promptly of these new serious and unexpected AE(s) or significant risks to subjects.

The Investigator must keep copies of all pertinent safety information on file including correspondence with Celgene and the IRB/EC. (See Section 15.3 for record retention information).

Celgene Drug Safety Contact Information:

For Celgene Drug Safety contact information, please refer to the Serious Adverse Event Report Form Completion Guidelines or to the Pregnancy Report Form Completion Guidelines.

12. DISCONTINUATIONS

12.1. Treatment Discontinuation

12.1.1. Events Leading to Suspension of Enrollment Pending DMC Evaluation

The following events in any subject will trigger a suspension of additional enrollment pending an evaluation by the Data monitoring Committee (DMC) of the event at an ad hoc meeting. Should such an event occur, the DMC will review the available data from the subject's history and the event itself as well as available data on all other previously treated subjects. The committee will recommend if it is appropriate to resume enrollment without study modifications, to resume enrollment with study modifications or to permanently discontinue further enrollment into the study. Operational details are specified in the DMC Charter.

- Identification of 1 or more subjects within a dosing treatment arm with ≥ Grade 3 allergic reaction that is suspected to be related to the IP.
- Identification of 1 or more subjects experiencing a suspected unexpected, treatmentrelated SAE (SUSARs) within 14 days following the initial dose of the IP suspected unexpected serious adverse reactions.
- Identification of 1 or more subjects with a new malignancy.

12.1.2. Mandatory Treatment Discontinuations

Should subjects experience any of the following events, they may not receive additional doses of PDA-002. They should stay on study however, and all scheduled evaluations are to be performed.

- A Grade 3 or higher allergic reaction within 24 hours of PDA-002 administration.
- An episode of symptomatic arterial vasospasm within 24 hours of PDA-002 administration. Examples include acute coronary ischemia and retinal artery spasm.
- An episode of new venous thrombosis within 3 days of PDA-002 administration.

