6.5.1. External Data Monitoring Committee

An external unblinded DMC will monitor safety and efficacy information to ensure subject safety in accordance with a separate charter. The external DMC will be comprised of members who are not involved in the day-to-day activities of the PDA-002 DPN study team. Data review packets will be forwarded to the DMC members for review at least 7 days prior to each scheduled DMC teleconference/meeting. Data will be current through 14 days prior to each scheduled DMC teleconference/meeting.

The external DMC will be convened to assess the benefit risk of PDA-002 when approximately 25% and 50% of subjects complete the Month 3 (Visit 6) assessment. Study enrollment will be ongoing during these scheduled reviews.

The external DMC chairman will be notified if an AE of medical interest should occur and will determine if a full DMC will need to be conveyed. During any period of deliberation by the external DMC on an AE of medical interest, a temporary hold on enrollment of new subjects will be instituted. The AEs of medical interest that would trigger this process are:

- Identification of 1 or more subjects within a dosing treatment arm with \geq Grade 3 allergic reaction that is suspected to be related to the IP.
- Identification of 1 or more subjects experiencing a suspected unexpected, treatmentrelated SAE (SUSARs) within 14 days following the initial dose of the IP suspected unexpected serious adverse reactions.
- Identification of 1 or more subjects with a new malignancy.

The sponsor will take appropriate action based upon the external DMC recommendation and this will be communicated to the investigators. The investigators will be responsible for notifying their Institutional Review Boards (IRBs). The external DMC will evaluate on an ongoing basis all available safety data, in particular all SAEs and their potential relationship to PDA-002. The external DMC may recommend modifications to enrollment or to the study design in order to ensure subject safety. Further explanation of the roles and responsibilities of the external DMC will be outlined in the external DMC charter.

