Administration Instructions. Under aseptic conditions, PDA-002 or placebo will be injected IM at 15 sites in one limb on Study Days 1, 29, and 57. The injection volume will be 0.30 mL per injection site. A 3.0 mL syringe with a 20 to 22-gauge 1.5-inch long needle will be used to inject the IP. The target region is suggested to be below the knee and above the ankle. Injections are suggested to be at least 1 cm apart horizontally and laterally and at a depth of approximately 1 to 4 cm. It is suggested that they be administered in a pattern of 3 x 5 injections around the leg, and injections should not be near a blood vessel. The administrator and the subject will be blinded to treatment.

A diagram of the recommended injection grid and anatomical site selection is provided in Appendix E.

The entire thawed IP must be administered within 4 hours of thaw start time and within 1 hour of the syringe fill time. In the event that it becomes medically necessary to stop the injections, the stop time of the injections as well as the time the injections are resumed must be noted in the eCRF and in the source documents. If less than the total injection volume is administered, the volume injected should be recorded and the sponsor should be notified.

Note: For this study, all \geq Grade 3 allergic reactions associated with the use of IP must be reported to Celgene Cellular Therapeutics as an SAE within 24 hours of the investigator's knowledge of the event.

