8.2.1. Discontinuation

The reason for discontinuation should be recorded in the eCRF and in the source documents. The decision to discontinue a subject remains the responsibility of the treating physician, which will not be delayed or refused by the sponsor. However, prior to discontinuing a subject, the investigator may contact the Medical Monitor and forward appropriate supporting documents for review and discussion. Of note, the investigator is not required to contact a medical monitor to discuss discontinuation or unblinding as the investigator has the ability to discontinue or rapidly unblind subjects.

Subjects who discontinue will have the procedures performed as listed in the Early Termination column as per the Table of Events (Table 1).

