12.1.3. Additional Treatment Discontinuations

The following events are considered sufficient reasons for discontinuing a subject from the investigational product and/or from the study:

- Adverse event(s)
- Withdrawal by subject
- Death
- Lost to follow-up
- Protocol violation
- Pregnancy

- Recovery
- Non-compliance with IP
- Study terminated by sponsor
- Physician decision
- Screen failure
- Technical problems
- Disease relapse
- Failure to meet randomization criteria
- Site terminated by sponsor
- Completed
- Other (to be specified in the eCRF)

The reason for discontinuation of treatment should be recorded in the eCRF and in the source documents.

The decision to discontinue a subject from treatment remains the responsibility of the treating physician, which will not be delayed or refused by the Sponsor. However, prior to discontinuing a subject, the Investigator may contact the Medical Monitor and forward appropriate supporting documents for review and discussion.

Subjects who discontinue will have laboratory assessments performed as specified in the Early Termination Column in the Table of Events (Table 1).

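### Section 12.1.2 requires dosing to stop after a Grade 3 or higher allergic reaction only if it occurs within 24 hours; for a later reaction suspected to be related to IP, nothing in the protocol expressly bars that subject's next dose

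*Combined protocol and SAP*

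**What the plan says.** Section 12.1.2 opens with "Should subjects experience any of the following events, they may not receive additional doses of PDA-002" and then lists three events, each with its own time limit. The allergy item is "A Grade 3 or higher allergic reaction within 24 hours of PDA-002 administration"; the others are symptomatic arterial vasospasm within 24 hours and new venous thrombosis within 3 days. None requires a causality judgement. Subjects stopped under this section remain on study and have all their scheduled evaluations.

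Section 12.1.1 suspends further enrolment when one or more subjects has an allergic reaction at or above "Grade 3 allergic reaction that is suspected to be related to the IP". It sets no onset limit. Section 6.5.1 repeats the trigger and describes the consequence: "a temporary hold on enrollment of new subjects will be instituted". After the suspension, Section 12.1.1 says: "The committee will recommend if it is appropriate to resume enrollment without study modifications, to resume enrollment with study modifications". The remaining listed option is to end enrolment permanently. Section 6.5.1 also lets the DMC recommend changes to the study design for subject safety.

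Sections 8.2 and 11.2.1 are reporting rules, again without an onset limit. The note in Section 8.2 says that reactions at or above "Grade 3 allergic reactions associated with the use of IP must be reported" to the sponsor as SAEs within 24 hours of the investigator learning of them.

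Outside the mandatory list, an adverse event is a sufficient reason to stop but not a required one. Section 12.1.3 says "The decision to discontinue a subject from treatment remains the responsibility of the treating physician", and Section 8.2.1 says "The decision to discontinue a subject remains the responsibility of the treating physician, which will not be delayed or refused by the sponsor".

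**The concern.** Suppose a subject has a Grade 3 allergic reaction 30 hours after a dose and the investigator suspects IP. Enrolment of new subjects is suspended until the DMC has looked at the event. The subject who reacted, and who carries the most direct evidence of risk, falls outside the mandatory stop and can be dosed again if the physician so decides.

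Re-exposure is a live question for this product. It is allogeneic and expresses HLA Class I (Section 8.1), and anti-HLA antibodies are measured before every dose (Table 1). Section 4.2 bases the schedule of three monthly doses on animal safety data. Section 1 describes one other study with monthly human dosing, and it is ongoing and blinded.

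**Working it through.** No statistical figure is involved, so the check sets the rules side by side and then counts visits and doses.

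**Rules for a Grade 3 or higher allergic reaction**

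| Section | Onset limit | Relation to IP required | Consequence |
|---|---|---|---|
| 12.1.2 | 24 hours | No | No further doses for that subject |
| 12.1.1, 6.5.1 | None | Suspected | New enrolment suspended; DMC review |
| 8.2, 11.2.1 | None | Associated with IP | SAE report |
| 12.1.3, 8.2.1 | None | No | Physician may stop dosing |

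Only the first row requires the affected subject's dosing to stop, and it ends at 24 hours. Section 13.2 mentions temporarily stopping IP, but in the setting of emergency unblinding and at the investigator's opinion.

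**The pre-thaw check.** Section 8.2 gives the three dosing days and then says thawing must wait until the subject is confirmed to meet the inclusion and exclusion criteria. Exclusion 26 is a history of hypersensitivity to components of the formulation; exclusion 6 is any condition creating unacceptable risk. If the check applies before every thaw, a severe IP-related reaction would probably fail it. Table 1, however, marks the eligibility criteria at Visit 1 only, and no text says that they are re-applied before doses 2 and 3. The point is ambiguous.

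**Time outside the mandatory rule.** Doses are on Days 1, 29 and 57.
- Dose intervals: 29 − 1 = 28 days and 57 − 29 = 28 days.
- Covered by the 24-hour rule: 1 day of each interval. Not covered: 28 − 1 = 27 days, with another dose still to come.

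**Next scheduled contact** (Table 1, ±3 days on each of these visits).
- After dose 1: Visit 3, 15 − 1 = 14 days later. Range 14 − 6 = 8 to 14 + 6 = 20 days.
- After dose 2: Visit 5, 57 − 29 = 28 days later. Range 28 − 6 = 22 to 28 + 6 = 34 days. Visit 5 is the dose 3 visit, so no scheduled visit lies between them.
- The required injection-site inspection runs to a minimum of 2 hours after the last injection (Section 6.2).

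If a site first hears of a late reaction to dose 2 at Visit 5, the decision on dose 3 falls at that same visit. The protocol text does not make that dose wait for DMC review.

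**Doses at stake.** After a reaction to dose 1: 3 − 1 = 2. After a reaction to dose 2: 3 − 2 = 1. After dose 3: none.

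**The case against.** The strongest reply is that the window is deliberate. All three mandatory stops are short and need no causality call, so the list reads as automatic stops for acute events, with later events left to clinical judgement. Nothing in the documents shows that 24 hours is too short. That stands as an explanation of the design, and the proposed change keeps the 24-hour rule. It does not explain why a late reaction judged related should hold back new subjects without also stopping the subject who had it.

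The second reply is that other safeguards cover the case: rapid SAE reporting, an ad hoc DMC review that includes the affected subject's history, AE assessment and an AE-directed examination at both later dosing visits, and a physician free to stop. A severe reaction may well be reported early, and the physician probably would stop. This lowers the practical risk and is the main reason for the modest priority. None of these safeguards is an express bar.

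A reader might go further than the documents allow in four ways:
- *That the sections contradict each other, or that the subject is unprotected.* They do not conflict. The rules govern different things, and discretionary and indirect protections exist, including a tenable reading of Section 8.2 that re-applies exclusions 6 and 26.
- *That no rule anywhere makes dosing wait for the DMC.* This can be said of the protocol only. Section 12.1.1 refers operational details to the DMC Charter, which is not available.
- *That placebo subjects fall outside the mandatory stops* because Section 12.1.2 names PDA-002. The protocol uses that name loosely for blinded product elsewhere (Section 8.2, Appendix E), and sites would probably read it as IP.
- *That an added rule would remove dependence on reporting and judgement.* It would not. The event must still be reported, and under Section 11.2.3 the investigator still decides whether it is suspected to be related.

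**Conclusion.** The gap is real and narrow. For a Grade 3 or higher allergic reaction more than 24 hours after dose 1 or dose 2 and suspected to be related to IP, the protocol suspends new enrolment and requires an SAE report but does not expressly bar that subject's next dose. Up to 2 of 3 doses are affected.

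The conclusion rests on the protocol text alone, and on treating the Section 8.2 check as ambiguous; a Charter rule, or a clear instruction to repeat the eligibility check before each thaw, would narrow or close the gap. Re-dosing after such a reaction would need several things to coincide in a trial of about 24 subjects, and no event rate or onset time is given from which to estimate the probability. The point concerns subject safety only; no statistical quantity changes. It is a cheap improvement of low to moderate priority.

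**What to change.** In Section 12.1.2, keep the 24-hour allergy item regardless of causality and add: *or a Grade 3 or higher allergic reaction at any time that is suspected to be related to IP*. Use the meaning of Suspected in Section 11.2.3, which is written in terms of IP and can be applied blinded. Once the event is reported and judged related, re-dosing is no longer discretionary.

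In the same edit, replace PDA-002 with IP in Section 12.1.2. This is a clarification only: placebo is the same vehicle without cells (Section 8.1), so the stops should plainly cover it.

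The cost is one wording amendment. A few subjects, possibly including some on placebo, may miss up to 2 of 3 doses, but they stay on study with all evaluations. Late allergic reactions not suspected to be related to IP would not trigger the added stop.
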